### **11.4.2 Extent of investigational medicinal product exposure**

Duration of IMP exposure is defined as: last dose date – first dose date + 1 day, regardless of unplanned intermittent discontinuations. The distribution of treatment duration will be summarized by treatment group using descriptive statistics.

### **11.4.3 Compliance**

A given administration will be considered noncompliant if the patient did not take the planned dose of treatment as required by the protocol. No imputation will be made for patients with missing or incomplete data.

Treatment compliance, above-planned and under-planned dosing percentages will be summarized descriptively (N, Mean, SD, Median, Min, and Max). The percentage of patients with compliance <80% will be summarized. In addition, the number and percentage of patients with at least 1 above-planned dosing administration will be given, as well as the number and percentage of patients with 0, (0, 20%], and >20% under-planned dosing administrations.

### **11.4.4 Analyses of efficacy endpoints**

#### **11.4.4.1 Analysis of primary efficacy endpoint(s)**

##### **Main statistical model and adjustment for covariates:**

Time to first relapse will be analyzed using a log-rank test with time to first relapse as the dependent variable, treatment group as a test variable, and region and pubertal status as covariates. The first RAP confirmed relapse, occurring from randomization (including relapses during the PK run-in (8 weeks) phase) to the end of the randomized, placebo-controlled study treatment period, will be included for analysis. Treatment effect as measured by the hazard ratio and its associated 95% confidence interval will be estimated using a Cox proportional-hazards model with factors for treatment group, region, pubertal status, age, and number of relapses in the year prior to randomization. Statistical significance will be claimed for the primary endpoint if the p-value for the 2-sided log-rank test is  $\leq 0.05$ .

##### **Handling of dropouts:**

Given the time to event analysis methodology, there is no impact on the analysis of the primary endpoint for patients experiencing a first relapse and moving to the open label teriflunomide treatment. Patients discontinuing double-blind treatment due to high MRI activity will be

censored at discontinuation. Patients who prematurely discontinue the study drug will be encouraged to continue study follow-up as planned according to the study flowchart. The main analysis for time to first relapse will include relapses during the placebo-controlled study treatment period. Relapses reported after study drug discontinuation (for non-relapse reason) will be included in a supportive analysis.

### **Sensitivity analysis:**

The following sensitivity analyses for the primary endpoint will be performed using the similar log-rank test and Cox proportional-hazards model as described above.

- Time to first confirmed relapse occurring after the PK run-in (8 weeks) phase but before the treatment discontinuation. The patients who have a relapse during the PK run-in (8 weeks) phase will be included in the analysis with the time to first relapse right censored at the time of treatment discontinuation.
- Time to first relapse (confirmed or not) after randomization during the study treatment.
- Time to first confirmed relapse including relapses during the PK run-in (8 weeks) phase and relapses reported after the study drug discontinuation and up to 96 weeks after randomization.
- Time to first confirmed relapse including high MRI activity meeting criteria for switching into open-label period as an equivalent to confirmed relapse event.

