EOT = end of treatment (EOT= First visit after last study drug intake), EDSS = expanded disability status scale, FS = functional score, BVMTR = brief visuospatial memory test-revised, SDMT=symbol digit modalities test, MRI = magnetic resonance imaging, PK = pharmacokinetic

- a Recommended windows: The window for obtaining biological samples at any given visit will be ±7 days. All other treatment period assessments should be completed within ±7 days of the scheduled visit date relative to the randomization visit. Post drug elimination follow-up visits should be ±7 days of scheduled visit relative to end of treatment.
- b Randomization visit up to 28 days from signing of informed consent.
- c End-of-treatment and premature discontinuation visit. This visit does not need to be performed when the patient switches to the open label period after a confirmed relapse or high MRI activity (as per protocol criteria). The drug elimination procedure must be initiated at this visit if applicable.

- d* For discontinuing treatment, 2 post drug elimination follow up visits should be scheduled 2 weeks and 4 weeks after study medication discontinuation and initiation of the drug elimination procedure. All patients who prematurely and permanently discontinue study medication will be asked to continue until the planned end of double-blind period.
- e* Re-consent must follow any RAP confirmed MS relapse for continuing in study when occurrence during PK run-in, for switching into open-label period when occurrence after PK run-in.
- f* To be prescribed at Visit 1 and report checked at Visit 2. MRI scan performed within 6 weeks prior to randomization can be used as the baseline MRI if performed according to the operations manual and accepted by the central reader.
- g* During the adverse event reporting process, specific questions about pulmonary symptoms and peripheral neuropathy symptoms will be asked. (Patients will be instructed to alert the treating physician of symptoms suggestive of immunodeficiency).

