### 11.1 DETERMINATION OF SAMPLE SIZE

The sample size calculation is based on the primary efficacy endpoint, time to first confirmed relapse after randomization. Assuming 60% of placebo patients will experience a relapse by 2 years, 165 children aged 10 to <18 years (110 teriflunomide and 55 placebo; including approximately 20% pre-pubertal patients or 10% of patients under the age of 13 years at time of inclusion into the study and at least 25% male patients) are needed for 80% power to detect a hazard ratio (teriflunomide versus placebo) of 0.5 (2-sided alpha 0.05). The 2-year rate of relapse in the teriflunomide group would be 36.8% and the corresponding hazard rates, assuming the time-to-relapse is exponentially distributed with a constant hazard rate, would be 0.4581 for placebo and 0.2291 for teriflunomide. The sample size is adjusted assuming 20% of patients discontinue the study in 2 years due to reasons other than relapse. Calculations are performed using nQuery Advisor 7.

The assumption for the percentage of placebo patients with relapse at 2 years is based on the combined data from the completed Phase III monotherapy adult studies (EFC6049/TEMPO and EFC10531/TOWER), where 58.7% of placebo patients aged  $\leq 30$  (n=167) experienced at least 1 relapse in a 2-year treatment period. Of note, the corresponding percentage was 38.7% in the 163 patients aged  $\leq 30$  treated with teriflunomide 14 mg.

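### As written, the post-run-in sensitivity analysis censors run-in relapsers at treatment discontinuation with no exception for a later confirmed relapse, which conflicts with its own event definition

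*Protocol*

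**What the plan says.** The rule is in protocol section 11.4.4.1, under Sensitivity analysis, with the same wording in the Clinical Trial Summary. The first of four sensitivity analyses takes as its event the first confirmed relapse after the run-in and before treatment discontinuation. The next sentence covers patients who relapse during the run-in: they stay in the analysis "with the time to first relapse right censored at the time of treatment discontinuation". It says nothing about a further confirmed relapse in such a patient.

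These patients can remain on blinded treatment. Footnote e of the double-blind flow chart (section 1.2) requires renewed consent "for continuing in study when occurrence during PK run-in", and section 9.8.6 agrees. Section 5.1 offers the relapse-triggered open-label switch only for a RAP-confirmed relapse after the run-in. A patient who relapses in Week 5 may therefore have a second confirmed relapse in, say, Week 40 and leave the double-blind period because of it.

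The primary analysis counts run-in relapses as events (section 11.4.4.1). The supplied SAP covers the open-label period; its section 2 places the double-blind analysis in a separate SAP.

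**The concern.** The two sentences of the bullet disagree about the same patient. A run-in relapser with a confirmed relapse in Week 40 has an event under the first sentence and is censored under the second. If that relapse leads to the open-label switch, the censoring date is set by the event under study, which is informative censoring.

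The documents give this analysis no stated purpose. It is, however, the only one of the four that looks solely at time after dose adjustment, and section 3.2.3 describes the run-in as given at the 7 mg adult-equivalent dose, with about 64% of steady state expected at 4 weeks. Two programmers working from this text could report different hazard ratios. The censoring sentence also says only that the patient had a relapse, not a confirmed one, so it is unclear whether an unconfirmed run-in event triggers it.

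**Working it through.** **Inputs from the protocol (section 11.1 unless noted).** "Assuming 60% of placebo patients will experience a relapse by 2 years"; hazards per year "would be 0.4581 for placebo and 0.2291 for teriflunomide"; 110 teriflunomide and 55 placebo patients; two-sided alpha 0.05; 80% power at a hazard ratio (HR) of 0.5; "The sample size is adjusted assuming 20% of patients discontinue the study in 2 years due to reasons other than relapse". Double-blind follow-up is up to 96 weeks and the run-in is the first 8 weeks (section 5.1).

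**Assumptions not in the documents.** Every run-in relapser continues blinded treatment; dropout is exponential and equal in both arms; the run-in HR is varied from 0.5 to 1.25; between-patient heterogeneity is gamma frailty with variance 0 or 1. The 30-day rule that merges symptoms into one relapse is ignored.

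**1. The plan's own figure.** Placebo hazard: -ln(0.4)/2 = 0.4581; half of it is 0.2291; 2-year teriflunomide rate: 1 - exp(-2 x 0.2291) = 36.8%. The Lachin-Foulkes formula uses P(λ) = λ/(λ+η) x [1 - exp(-2(λ+η))], φ(λ) = λ²/P(λ) and mean hazard (2 x 0.2291 + 0.4581)/3 = 0.3054:

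N = [1.960 √(4.5 φ(0.3054)) + 0.8416 √(1.5 φ(0.2291) + 3 φ(0.4581))]² / (0.4581 - 0.2291)²

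With η = -ln(0.8)/2 = 0.1116, N = 167.5; with η = 0.10, N = 165.8. The stated 165 is reproduced closely enough to use these inputs.

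**2. Run-in relapsers, run-in HR 0.5.** Eight weeks is 56/365.25 = 0.1533 years.
- Placebo: 1 - exp(-0.4581 x 0.1533) = 6.78%, or 3.7 of 55.
- Teriflunomide: 1 - exp(-0.2291 x 0.1533) = 3.45%, or 3.8 of 110.

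**3. Events after the run-in.** With 96 weeks = 1.8398 years, the probability of a post-run-in event is λ/(λ+η) x exp(-0.1533η) x [1 - exp(-(λ+η) x 1.6865)]: 0.488 on placebo and 0.289 on teriflunomide. Expected events are 55 x 0.488 + 110 x 0.289 = 26.8 + 31.8 = 58.6. Lost under the literal rule: 3.73 x 0.488 = 1.8 placebo and 3.80 x 0.289 = 1.1 teriflunomide. Simulation of 1.2 million patients gave 1.87 and 1.09, so about 3.0 in total.

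**4. Hazard ratio under the literal rule.** If patients leave at the later relapse, risk sets do not change and each arm loses a share of events equal to its run-in relapse probability: 0.50 x (1 - 0.0345)/(1 - 0.0678) = 0.518. Simulation agrees. If they stay on treatment and count as event-free until discontinuation, it gives 0.531.

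**5. Dependence on the run-in effect** (simulation, no frailty; counts scaled to 55/110):

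| Run-in HR | Run-in relapsers (pbo/teri) | Later events lost (pbo/teri) | HR, later relapses counted | HR, literal, leave | HR, literal, stay |
|---|---|---|---|---|---|
| 0.5 | 3.72 / 3.76 | 1.87 / 1.09 | 0.500 | 0.518 | 0.531 |
| 0.75 | 3.71 / 5.60 | 1.82 / 1.67 | 0.501 | 0.509 | 0.519 |
| 1.0 | 3.70 / 7.39 | 1.80 / 2.15 | 0.501 | 0.501 | 0.508 |
| 1.25 | 3.69 / 9.15 | 1.80 / 2.65 | 0.498 | 0.489 | 0.495 |

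**6. Power of this analysis** (4000 simulated trials of 165). With run-in HR 0.5: 74.0% when later relapses count, 67.1% (leave) or 64.5% (stay) under the literal rule. With run-in HR 1.0: 74.8% against 71.5% or 69.4%; events are still lost although the HR hardly moves.

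**7. Heterogeneity.** With frailty variance 1, 0.564 becomes 0.591-0.605 at run-in HR 0.5, and 0.563 becomes 0.556-0.564 at run-in HR 1.0. The step from 0.50 to 0.564 comes from the assumed frailty, not from the censoring rule.

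**8. Scale.** The simulated standard error of the log HR is 0.265. The shifts are ln(0.518/0.50) = 0.035 and ln(0.531/0.50) = 0.060, or 0.13 and 0.23 standard errors.

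**The case against.** The strongest reply is that the sentence need not be read literally. The bullet defines the event first, and a run-in relapser with a later confirmed relapse meets that definition. The second sentence may mean only that the run-in relapse is ignored and that, absent a later event, the patient is censored like anyone else. The separate double-blind SAP may say so. This reading is possible, so it cannot be said that the sponsor's analysis discards these relapses. But the protocol text does not choose between the readings, and its plain wording favors the one that contradicts the event definition.

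A reader might also infer that the rule always pulls the hazard ratio toward 1, or removes events selectively from placebo. The documents support neither. The direction needs proportionally more run-in relapsers on placebo, and the lower dose and below-steady-state exposure in section 3.2.3 make a run-in effect weaker than 0.5 plausible. Losses fall in both arms, about 1.9 and 1.1 events even at a run-in HR of 0.5. At a run-in HR of 1 the larger count is on teriflunomide.

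It is also fair to say that the effect is small, that some run-in relapsers may not continue (re-consent must cover alternative therapies, section 9.8.6), and that section 11.4.4.3 attaches the significance claim to the primary analysis alone. These objections lower the severity; they do not remove the contradiction.

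**Conclusion.** The point holds as a minor one. Followed as written, the rule censors patients who have the event being analyzed. At the planning hazards, with a constant HR of 0.5 and all run-in relapsers continuing, that costs about 3 of 59 events. The HR moves by about 0.02-0.03, and power for this one supportive analysis drops by roughly 7 to 10 percentage points. Neither the direction nor the size of the shift is fixed, because both depend on the unknown run-in effect. A reader should not carry the concern over to the primary result, which counts run-in relapses. Whether the analysis was programmed this way cannot be determined without the double-blind SAP.

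**What to change.** Replace the censoring sentence in section 11.4.4.1 and in the Clinical Trial Summary, and in the double-blind SAP if it carries the same wording, with:

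> Relapses during the run-in, confirmed or not, are not counted as events and do not end follow-up. The first RAP-confirmed relapse after Week 8 and before treatment discontinuation is the event for all patients, including those with a run-in relapse. Only patients without such a relapse are censored at treatment discontinuation.

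No Week 8 landmark or change of population is needed. No event counts before Week 8, so resetting the clock leaves the Cox and log-rank risk sets unchanged, and patients gone by then enter none of them.

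The cost is one sentence and a small change to the event derivation. Amended Protocol 3 (2 August 2018) reports enrolment complete, so 96 weeks of double-blind treatment would have ended by about June 2020 and the analysis may already have been run. If so, the report should state which reading was programmed and give the result under the other as well.

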### **Subgroup analysis:**

Subgroup analyses will be performed for the primary efficacy endpoint. The results will be presented for demographic (eg, pubertal status, age, sex, race) and other (eg, MS history, region) subgroups. One of these analyses will include patients with relapsing-remitting form of MS versus other forms. The detailed information will be provided in the Statistical Analysis Plan (SAP).

#### **11.4.4.2 Analyses of secondary efficacy endpoints**

The proportion of patients relapse-free at Weeks 24, 48, 72 and 96 will be estimated based on Kaplan-Meier methods. Interval estimates will be calculated using 95% point wise confidence intervals.

The number of new or enlarged T2-lesions per MRI scan will be analyzed using a negative binomial regression model. The model will include the total number of new or enlarged T2-lesions as the response variable, with treatment group, region, pubertal status and age as covariates. In order to account for different numbers of MRI scans performed among patients, the log-transformed number of scans will be included in the model as an offset variable. The estimated number of lesions per scan and associated 2-sided 95% CI will be provided for each treatment group. The relative risk, 2-sided 95% confidence interval (CI) and p-value will be provided for comparing teriflunomide to placebo.

The number of T1 Gd-enhancing lesions per MRI scan and the number of new T1 hypointense lesions per MRI scan will be analyzed using a similar negative binomial regression model as described above for T2 lesions.

To reduce the impact of potential outliers, an ordinal logistic regression model including treatment group, region, pubertal status and age will also be used to analyze these endpoints. The following categories for the number of lesions, 0, 1, 2, 3-4 and  $\geq 5$ , are considered and will be further defined in the SAP.

A Poisson regression model with a robust error variance will be used in sensitivity analyses.

Change from baseline in volume of T2 lesions, T1 hypointense lesions and brain atrophy will be analyzed using a mixed-effect model with repeated measures (MMRM) approach with appropriate transformation if necessary. The proportion of patients free of new or enlarged T2-lesions at Weeks 48 and 96 will be summarized based on all patients having an MRI at these time points. More details will be provided in the SAP.

The change from baseline in cognitive outcomes at each visit will be analyzed descriptively.

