#### **MRI**

All brain scans will be reviewed and interpreted by one or more neuroradiologists at an independent, central facility with no access (ie, blinded) to treatment assignment thereby avoiding bias.

An MRI manual explaining the instructions for standard image acquisition requirements, data transfer, archiving and shipping, and outlining the phantom data approval process will be provided to all centers.

MRI should not be conducted within 2 weeks of steroid administration due to potential interference.

In case of at least 5 new/enlarged T2 lesions at the MRI of Week 24, an additional MRI will be performed at Week 36.

Then, in case of:

- At least 9 new/enlarged T2 lesions at Week 36, or,
- At least 5 new/enlarged T2 lesions on each of the 2 consecutive MRI scans of Week 36 and Week 48, or,
- At least 5 new/enlarged T2 lesions on each of the 2 consecutive MRI scans of Week 48 and Week 72.

Patients will have the option to continue in an open label teriflunomide treatment arm.

(Note: new/enlarged refer to previous scan)

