### 8.1.2 Secondary efficacy

The secondary efficacy endpoints for the 96-week double-blind treatment period are the following:

- Proportion of relapse free patients at 24, 48, 72 and 96 weeks.
- MRI endpoints:
  - Number of new/newly enlarged T2 lesions,
  - Number of T1 Gd-enhancing T1 lesions,
  - Change in volume of T2 lesions,
  - Change in volume of T1 hypointense lesions,
  - Number of new hypointense T1,
  - Proportion of patients free of new or enlarged MRI T2-lesions at 48 weeks and 96 weeks,
  - Brain atrophy.

The number of new/newly enlarged T2 lesions and the number of T1 Gd-enhancing T1 lesions will be considered the key secondary imaging endpoints.

- Cognitive outcome measured by the SDMT and Cognitive Battery Tests (15, 4), when available.
- Teriflunomide PK.

Exploratory endpoint: proportion of disease-free patients.

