Long-term safety of teriflunomide exposure will also be analyzed by including all teriflunomide exposure, ie, from randomization in the double-blind period in the teriflunomide group and from start in the open-label period in the placebo group, for the complete study population analyzed in one overall group. Key safety analyses on TEAEs, SAEs, TEAEs leading to treatment discontinuation and AESIs.

Safety Subgroup Analysis

Safety subgroup analyses will be performed for key tables of TEAEs/SAEs/AESIs and TEAEs leading to treatment discontinuation during the treatment-emergent adverse event period in the open-label period by:

- Intrinsic factors
 - Age group at study consent of the double-blind period (<13, ≥13 years)
 - Gender
 - Race
 - Pubertal status (at study consent, and at disease onset)
 - Baseline weight group in the double-blind period (≤40, >40 kgs)
 - MS subtypes (relapsing-remitting MS, other forms)
 - High disease activity at baseline (defined as 2 or more relapses in the past year of screening, and 1 or more Gadolinium enhancing lesions on baseline MRI of the double-blind period) (Yes, No)
- Extrinsic factors
 - Region (as defined in [Section 2.5.5](#)).

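### The protocol prints no baseline MRI activity term in the double-blind lesion-count models for the two key secondary imaging endpoints: a modest precision issue, to be settled by checking the double-blind SAP

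*Protocol*

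**What the plan says.** For the double-blind period, Protocol 11.4.4.2 (repeated in the Clinical Trial Summary) fits a negative binomial model to the total number of new or enlarged T2 lesions. The log number of scans is the offset, and the model is specified "with treatment group, region, pubertal status and age as covariates". The companion analysis against outliers is an "ordinal logistic regression model including treatment group, region, pubertal status and age". The Gd-enhancing T1 and new T1 hypointense counts "will be analyzed using a similar negative binomial regression model as described above for T2 lesions", with no covariate list of their own. The robust Poisson sensitivity analysis also has none.

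Protocol 8.1.2 says that the T2 and Gd-enhancing counts "will be considered the key secondary imaging endpoints". Protocol 11.4.4.3 plans no multiplicity adjustment for secondary outcomes.

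Baseline data exist. Protocol 8.1 (MRI) says: "All brain scans will be reviewed and interpreted by one or more neuroradiologists at an independent, central facility". The Section 1.2 flow chart requires a baseline MRI, and its footnote f allows a recent one: "MRI scan performed within 6 weeks prior to randomization can be used as the baseline MRI". SAP 2.4.5.1 already uses baseline enhancement as one part of a safety subgroup: "1 or more Gadolinium enhancing lesions on baseline MRI of the double-blind period".

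The supplied SAP covers the open-label period. Its count model (2.4.4.2.3) lists the same four terms. Its Section 2 says that the double-blind analysis was addressed in a separate SAP.

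**The concern.** Patients differ widely in how readily they form lesions, and a baseline measure of lesion activity is a natural candidate to explain part of that spread. If it does, leaving it out makes the interval on the teriflunomide/placebo ratio wider than it need be, with only 55 placebo patients planned. The sponsor cared about precision here: the reasons for Amendment 1 (Protocol 17.9) say that a scan was added partly to raise power on the MRI endpoints. The principle is also not foreign to the plan, since the Cox model for the primary hazard ratio has "factors for treatment group, region, pubertal status, age, and number of relapses in the year prior to randomization".

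What is at stake is the width of two secondary intervals. The validity of the comparison is not in question.

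**Working it through.** **1. The plan's own figure.** The only sample-size figure is 165 for time to first relapse. The hazards reproduce: -ln(0.4)/2 = 0.4581, and half of that is 0.2291. Exponential formulas with 20% dropout over 2 years give 164 to 168 patients, and simulated log-rank power at 110:55 is 79.9%. This has no bearing on the lesion models, for which the documents give no mean, dispersion, correlation or power. Everything below rests on assumed inputs.

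**2. Closed form, noise-free baseline (roughly an upper bound).** With placebo mean mu0, dispersion k, rate ratio RR, and baseline explaining a share R2 of between-patient variance in lesion rate:

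Var(log RR) = (1/mu0 + k(1-R2))/55 + (1/(mu0 x RR) + k(1-R2))/110

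For mu0 = 5, k = 1, RR = 0.6, R2 = 0: 1.2/55 + 1.333/110 = 0.0339, so SE = 0.184. At R2 = 0.10, 0.25 and 0.40 the SE is 0.177, 0.165 and 0.152.

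**3. Simulation with a real, noisy baseline count.** There were 2,000 trials per case, 55 placebo and 110 teriflunomide patients, RR 0.6, and equal scans per patient. Six (mean, k) cases were run: (2, 0.5), (2, 1.5), (5, 1), (10, 1.5), (15, 0.5), (15, 2). Baseline Gd count was Poisson with mean 1.5 or 3 times a patient frailty. Both models held treatment, five regions, pubertal status and age; one added log(baseline count + 1). Fall in the empirical SE of log RR:

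| R2 | Gamma frailty, range (median) | Lognormal frailty, range (median) |
|---|---|---|
| 0 | change of about 1% or less, either way | change of about 1% or less, either way |
| 0.10 | 0.3-2.4% (1.0%) | 0.2-7.1% (4.3%) |
| 0.25 | 0.8-6.4% (3.5%) | 1.8-14.5% (9.2%) |
| 0.40 | 2.2-10.5% (6.6%) | 3.1-23.3% (13.7%) |

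Gamma frailty matches the planned negative binomial model. Example (gamma, mean 5, k 1, baseline mean 3): SE 0.1972 unadjusted; 0.1977, 0.1926, 0.1862 and 0.1765 adjusted at R2 = 0, 0.10, 0.25 and 0.40. Median RR was 0.594-0.610 across all fits, so the added term did not shift the effect.

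**4. Width of the interval that would be reported.** Mean model-based CI width on the log scale falls by 0.9-2.7% (gamma) or 0.8-4.5% (lognormal) at R2 = 0.10, and by 2.2-6.9% or 2.0-10.5% at 0.25.

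**5. Early exits.** Patients may switch at a confirmed relapse after Week 8 or at high MRI activity, and Section 1.2 footnote c requires no EOT visit at the switch. At the protocol hazards, first relapses between Weeks 8 and 24 number
- placebo: 55 x (exp(-0.4581 x 8/52) - exp(-0.4581 x 24/52)), about 7;
- teriflunomide: 110 x (exp(-0.2291 x 8/52) - exp(-0.2291 x 24/52)), about 7.

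Some of these patients may have no post-baseline double-blind scan. A 3,000-trial rerun (mean 5, k 1, baseline mean 3) added relapse exits and 20% dropout, with no exit scan. At R2 = 0.10 and 0.25 the gamma gains went from 2.2% to 1.9% and from 5.2% to 4.5%. The lognormal gains went from 3.9% to 3.6% and from 8.8% to 7.7%.

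**6. Timing.** Enrolment was complete by 2 Aug 2018 (Protocol 17.9, reason for amended protocol 3). Adding 96 weeks of treatment, 4 weeks of screening as an allowance and 4 weeks of follow-up gives 30 Jul 2020. Lock about 28 days later (SAP 1.1) gives about 27 Aug 2020, 105 days before this protocol version (10 Dec 2020).

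**The case against.** The strongest objection is that the governing document is missing. The double-blind SAP may already name a baseline term, and Protocol 11.4.4.2 defers details to the SAP. That stands. A reader might infer from the four terms in the open-label SAP that the double-blind SAP has the same list; the documents make this plausible but do not show it.

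The printed list is also coherent: region and pubertal status reflect the stratification factors (country pooled into regions), and two alternative count analyses are planned. That stands too, and it makes this an improvement to consider, not an error.

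A reader might infer from the Cox model that the plan treats its primary and imaging endpoints inconsistently. The contrast is only partial. Significance on the primary endpoint rests on a log-rank test with region and pubertal status alone, so that test has no baseline activity term either.

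The gain may be negligible. In the weakest gamma case (mean 15, k 2) the SE goes from 0.2467 to 0.2493 at R2 = 0 and only to 0.2458 at R2 = 0.10. R2 may well be low, because the baseline scan can be up to 6 weeks old and some prior MS drugs need stop only 1 month before randomization (Protocol 6.3.2).

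For T2 lesions the case is weaker. New or enlarged lesions are counted against a previous scan and have no baseline count. A Gd count would be a proxy, and its link to T2 was not modelled separately. The SAP subgroup shows a yes/no use of baseline enhancement, not a derived count.

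**Conclusion.** The point holds as a minor, precision-only matter. The protocol prints no baseline MRI activity term for either key secondary imaging endpoint. Under the assumed inputs, the SE of the log rate ratio falls by roughly 0-7% if baseline explains about 10% of between-patient variance and by about 1-15% at 25%. The fall is somewhat smaller with relapse exits and dropout. It is about nil, within about 1% either way, if baseline is not prognostic.

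Three stronger readings are not supported:
- **Bias.** Under randomization, omitting a prognostic covariate does not bias the comparison, and no multiplicity-controlled claim depends on these models.
- **Lost patients.** Converting the SE falls into an equivalent number of patients would suggest a precision that the inputs lack: the frailty distributions are assumed, and the falls are in empirical SE, not in the reported interval.
- **Larger gains.** Closed-form falls of about 4-5% at R2 = 0.1 and 11-16% at 0.3, for means of 3-20 and dispersion of 0.8-2.5, assume a baseline measured without noise. They should not be read as expected gains.

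**What to change.** 1. Check the covariate list in the separate double-blind SAP. If it already names a baseline MRI term, only the protocol wording needs aligning.
2. If not, add log(baseline Gd-enhancing count + 1) to the Gd-enhancing T1 model. State one missing-baseline rule, for example the overall median, applied alike in both arms.
3. The same term in the new/enlarged T2 model is optional, as a proxy whose prognostic value is not shown.
4. If the double-blind data are still blinded, specify this before lock. If they are unblinded, which the dates make likely although no lock date is printed, keep the planned four-covariate model as the reported result. Show the adjusted fit beside it as a labelled post hoc sensitivity analysis.

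The cost is one extra fit per endpoint from data already collected, plus the missing-baseline rule. After unblinding, the covariate form and the imputation rule are chosen post hoc, and the result must carry that label. If baseline proves uninformative, the simulated SE changes by about 1% or less.
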